### **Compliance**

There will be a summary of the number of subjects receiving study drug and dose at each study drug administration visit. This will be repeated on the cumulative number of doses.

When computing compliance at each study drug administration visit, the denominator will include all subjects who have not prematurely discontinued the study drug prior to the scheduled study drug injection. Subjects who have prematurely discontinued the study drug but have not prematurely discontinued the study are not used in the denominator.

## **10.0 Efficacy Analysis**

### **10.1 General Considerations**

The efficacy analysis will be performed for ITT population. The efficacy analysis will use the data from this study with baseline from Study 1311.2 and will be summarized by treatment groups in Study 1311.2.

Continuous variables will be summarized by the number of observations, mean, standard deviation, median, minimum, maximum, as well as the 95% confidence intervals (CIs) of the mean values. Categorical variables will be summarized by counts and percentages, as

well as the 95% CIs of the percentages. No statistical tests will be performed in this study.

No missing data imputation will be applied. All efficacy analyses will be based on Observed Cases (OC) analysis, and thus a subject who does not have an evaluation at the analysis time point will not be included.

All endpoints will be analyzed up to the last visit at least one subject has observed measurements of that variable.

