3.3.4 Removal of patients from therapy or assessments

3.3.4.1 Removal of individual patients

An individual patient is to be withdrawn from the trial if:

- The patient withdraws consent, without the need to justify the decision.
- Clinically important acute or chronic infections including hepatitis, HIV and tuberculosis (including latent tuberculosis), or a positive interferon gamma release assay (IGRA) testing for tuberculosis (cf. [Table 5.2.3: 1](#)) according to test at the roll-over visit.
- The patient is no longer able to participate for other medical reasons (e.g. pregnancy, surgery, AEs or other diseases).

A patient can be withdrawn after discussion between sponsor and investigator if eligibility criteria are being violated or if the patient fails to comply with the protocol (e.g. non-attendance at study assessments). Note: Patients using restricted medications (cf. [Section 4.2.2](#)), will continue to be followed up to collect safety data but their efficacy and PD endpoints assessed after administration of restricted medications will not be considered for analysis.

If a patient withdraws from the study after informed consent, this will be documented and the reason for withdrawal will be recorded in the case report form (CRF). This data will be included in the trial database and will be reported. At the time of discontinuation a complete end of treatment (Extended EOT) evaluation should be performed according to [Flow Chart](#) and the patient will subsequently enter a follow up period of 12 weeks, until a final Extended EOS visit is performed. If the decision to discontinue study participation is taken in between study visits in the treatment period, an Extended EOT visit is to be scheduled at the earliest convenience and by the latest at the next upcoming visit according to [Flow Chart](#) and the information will be recorded in the CRFs.

Proprietary confidential information.

© 2018 Boehringer Ingelheim International GmbH or one or more of its affiliated companies. All rights reserved.

This document may not - in full or in part - be passed on, reproduced, published or otherwise used without prior written permission.

If the decision to discontinue is taken in the 12 week follow up period, an early Extended EOS visit is to be scheduled at the earliest convenience. The procedures described at Extended EOS will be performed and the information will be recorded in the CRFs. The withdrawals will be discussed in the final report of the study.

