5.1.1.3 Further endpoints of efficacy

Additional efficacy analyses will include, but are not limited to, the following:

- achievement of PASI₅₀ at all Extended dosing period visits where PASI is collected
- achievement of PASI₇₅ at all Extended dosing period visits where PASI is collected
- achievement of PASI₉₀ at all Extended dosing period visits where PASI is collected
- achievement of PASI₁₀₀ at all Extended dosing period visits where PASI is collected
- achievement of sPGA of clear or almost clear at all visits where sPGA is collected
- time to loss of PASI₅₀, which is a time to failure endpoint. This will be repeated using PASI₇₅, PASI₉₀, and PASI₁₀₀ as the endpoint.
- sPGA will be evaluated in terms of time to loss of response which is defined as a score exceeding 1, and will be evaluated as a time to failure endpoint
- change from baseline in Pain-VAS (in subgroup of patients with psoriatic arthritis only where baseline VAS is from 1311.2)
- mean DLQI scores at all Extended dosing period visits where PASI is collected

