7.3.2 Secondary analyses

The same methods as discussed for the primary analyses will be used to analyse all binary secondary and other endpoints, which include achievement of PASI50 / PASI75 / PASI90 / PASI100 at all Extended dosing period visits where PASI is collected and achievement of sPGA of clear or almost clear at all Extended dosing period visits where sPGA is collected.

Time to loss of PASI₅₀ / PASI₇₅ / PASI₉₀ / PASI₁₀₀, and time to loss of sPGA of clear or almost clear will be analysed using a Kaplan-Meier estimate.

Percent change from baseline in Pain-VAS for patients with non-zero baseline will be summarized descriptively at time points collected.

DLQI will be summarized descriptively at time points collected.

Additional information on these analyses will be provided in the trial statistical analysis plan.

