7.4 HANDLING OF MISSING DATA

Use of inappropriate concomitant medication to treat psoriasis will be considered as failure when deriving response variables, e.g. PASI₉₀.

Further details on the handling of missing data will be provided in the Trial Statistical Analysis Plan.

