### **Definition of Missing Data Imputation**

No global imputation is taking place at the database level. Efficacy related imputations are outlined in Section 10.0. There is no imputation for missing values in the safety analyses.

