#### **7.4 Protocol Deviation**

Number and percentage of subjects who reported at least one of the following protocol deviation categories will be provided.

- Subject entered into the study even though she/he did not satisfy entry criteria
- Subject who developed withdrawal criteria during the study and was not withdrawn
- Subject who received wrong treatment or incorrect dose
- Subject who received excluded or prohibited concomitant

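### The SAP omits, without saying so, the protocol's rule for responses reached on prohibited psoriasis medication and its Kaplan-Meier analyses of time to loss of response

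*SAP*

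**What the plan says.** **Prohibited medication.** Protocol 7.4 gives a rule for deriving response, naming PASI90 as an example: "Use of inappropriate concomitant medication to treat psoriasis will be considered as failure when deriving response variables". Protocol 3.3.4.1 deals with patients who use restricted medication. It keeps them in safety follow-up, but "their efficacy and PD endpoints assessed after administration of restricted medications will not be considered for analysis". SAP 10.1 states only: "No missing data imputation will be applied. All efficacy analyses will be based on Observed Cases (OC) analysis". Neither medication rule appears in SAP 10.1–10.3. Prohibited medication enters the SAP only as a deviation category in SAP 7.4 ("Subject who received excluded or prohibited concomitant"). The missing-data paragraph in SAP 6.0 says "Efficacy related imputations are outlined in Section 10.0", but Section 10.0 describes no imputation.

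**Loss of response.** Protocol 5.1.1.3 lists time to loss of PASI50, repeated for PASI75, PASI90 and PASI100. For sPGA it specifies "time to loss of response which is defined as a score exceeding 1, and will be evaluated as a time to failure endpoint". Protocol 7.3.2 names the method for the PASI and sPGA endpoints alike ("time to loss of sPGA of clear or almost clear will be analysed using a Kaplan-Meier estimate") and adds: "Additional information on these analyses will be provided in the trial statistical analysis plan". The synopsis and Protocol 7.1 also list time to loss of response. SAP 10.2 and 10.3 contain only proportions and changes from baseline by visit.

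**The concern.** PASI90 at Week 48 of the Extended dosing period is the primary efficacy endpoint, and the documents leave open how a response on prohibited medication is scored. Such data can exist: users stay in follow-up, and Protocol 3.1 has PASI scored at every visit. A programmer working from SAP Section 10 would count these responses as successes.

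Protocol 2.2 makes durability of response part of the trial's purpose. The analyses that follow individual patients to loss of response are the ones missing from the SAP.

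The SAP does explain a departure elsewhere: Section 11.3.2 gives a reason for grading laboratory values on a different scale from the protocol's. Nothing comparable is said here, so a reader cannot tell a deliberate change from an oversight.

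**Working it through.** The plan has no figure of its own to reproduce. The check is a comparison of the texts, followed by illustrations on assumed counts.

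**1. Medication rule, side by side**

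| Source | An observed PASI90 after prohibited medication |
|---|---|
| Protocol 7.4 | Stays in the denominator, counted as failure |
| Protocol 3.3.4.1 | Leaves numerator and denominator |
| SAP 10.1–10.3 | No rule; counted as success if followed literally |

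The two protocol rules also differ in scope. Section 7.4 concerns medication used to treat psoriasis. Section 3.3.4.1 refers to the restricted list, which in Table 4.2.2.1:1 also covers drugs that interfere with or aggravate psoriasis.

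**2. Effect on Week 48 PASI90**

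Let *n* be the patients observed at Week 48, *R* the observed responders, *u* the observed users of prohibited medication and *r* the users who are responders.

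- SAP as written: *R*/*n*
- Failure rule: (*R* − *r*)/*n*
- Exclusion rule: (*R* − *r*)/(*n* − *u*)

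Assume *n* = 80 and *R* = 66, so the SAP gives 66/80 = 82.5%.

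| Rule | Case | Result |
|---|---|---|
| Failure | *r* = 0 | 66/80 = 82.5% |
| Failure | *r* = 5 | 61/80 = 76.3% |
| Failure | *r* = 10 | 56/80 = 70.0% |
| Exclusion | *u* = 5, *r* = 5 | 61/75 = 81.3% |
| Exclusion | *u* = 5, *r* = 0 | 66/75 = 88.0% |

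Under the failure rule each responding user costs 1/80 = 1.25 points, so the SAP result is never below the failure-rule result. Against the exclusion rule the direction depends on the users: the two agree only when *r*/*u* = 66/80 = 0.825.

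The failure-rule rows keep *n* at 80, which assumes that a user with no Week 48 assessment is left out.

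**3. Can visit proportions stand in for time to loss?**

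Take patients with PASI90 at Extended Visit 2 (Week 12), assume full attendance, and let a proportion *p* show PASI90 at each of Weeks 24, 36 and 48. The share with no loss through Week 48 has these limits:

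- Upper limit *p*: the same patients fail at every visit.
- Lower limit 1 − 3(1 − *p*): different patients fail at each visit.

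| *p* | Lower | Upper | Out of 80 such responders |
|---|---|---|---|
| 0.80 | 1 − 3(0.20) = 0.40 | 0.80 | 32 to 64 |
| 0.90 | 1 − 3(0.10) = 0.70 | 0.90 | 56 to 72 |

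Identical visit-by-visit results are therefore compatible with very different durability. The SAP's proportions are also taken over all observed subjects, not earlier responders, so they say less still about loss of response.

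**The case against.** The strongest reply is that the SAP is silent rather than contradictory. The observed-case sentence sets policy for missing data, whereas the medication rule reclassifies observed values. The SAP presents itself as elaborating the protocol's methods, so its silence does not revoke Protocol 7.4. Time to loss sits among the further endpoints, in a trial whose primary objective is safety, and response at every visit gives a population view of maintenance. The counts used above are invented, and the lower durability limit is an extreme case.

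Much of this is right as qualification:

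- Observed-case handling of missing visits is not a breach, because Protocol 7.4 leaves further missing-data detail to the SAP.
- The pointer in SAP 6.0 is an editorial matter.
- The figures show that a difference is possible, not that it is likely. If no responder used prohibited medication, the failure rule changes nothing.

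It does not remove the point. The SAP says it guides the programming, and as written it produces neither a medication rule nor any time-to-loss output. Reading the protocol back into the SAP does not help with medication either, because the protocol gives two different rules.

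**Conclusion.** The concern holds, and both parts should be fixed. The two omissions and the conflict between Protocol 7.4 and 3.3.4.1 are plain on the text. The size of the effect on results is unknown, because the documents give no rate of prohibited-medication use. Relative to Protocol 7.4, the Week 48 PASI90 rate under the SAP is equal or higher, by 1.25 points per responding user if 80 patients are observed. Relative to Protocol 3.3.4.1 it can move either way. For durability, the planned time-to-loss result is absent and cannot be recovered from the visit proportions. With no hypothesis testing, the consequence is for the reported estimates, not for power or type I error.

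**What to change.** 1. **Reconcile Protocol 7.4 and 3.3.4.1, and state the rule in SAP 10.1.** For the binary PASI and sPGA endpoints the natural choice is the failure rule, since it is the statistical section's own rule for response variables. The text should:
   - apply it from the start of the medication and say when, if ever, it ends;
   - say how a user with no Week 48 assessment is handled;
   - exempt the topical use that Protocol 4.2.1 permits;
   - say whether the exclusion in Protocol 3.3.4.1 applies to DLQI and Pain-VAS.
2. **Restore the Kaplan-Meier time-to-loss analyses in SAP 10.3** with the protocol's definitions: response below the PASI threshold in question, and sPGA above 1. Specify the risk set, time origin and censoring, including censoring at roll-over to M15-997, because the protocol fixes none of these. If the analyses are dropped on purpose, say so and give the reason.
3. **Tidy the SAP 6.0 cross-reference** so that it no longer promises imputations. A Week 48 missing-data sensitivity row beside the observed-case result would be optional.

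The cost is SAP wording, one protocol clarification and a few extra outputs. PASI and sPGA are already collected, and Protocol 4.2.1 has concomitant and rescue therapies recorded in the eCRF. The deviation category in SAP 7.4 helps identify users, but a visit-level rule needs medication dates and a judgement on indication. The reported PASI90 rate may come out somewhat lower.

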## **10.2 Key Efficacy Variables**

The following key efficacy variables will be summarized at Week 48:

- Proportion of subjects achieving  $\geq 90\%$  reduction in Psoriasis Area and Severity Index (PASI) score (PASI 90)
- Proportion of subjects achieving the Static Physician Global Assessment (sPGA) score of clear or almost clear
- Proportion of subjects achieving  $\geq 50\%$  reduction in PASI score (PASI 50)
- Proportion of subjects achieving  $\geq 75\%$  reduction in PASI score (PASI 75)
- Proportion of subjects achieving 100% reduction in PASI score (PASI 100)
- Proportion of subjects achieving the sPGA score of clear

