Clinical Trial Protocol

Doc. No.: c02318676-08

EudraCT No.:	2014-001687-36	
BI Trial No.:	1311.13	
BI Investigational Product(s):	BI 655066	
Title:	An open label extension trial assessing the safety and Efficacy of BI 655066/ ABBV-066/risankizumab administered subcutaneously in patients with moderate to severe chronic plaque psoriasis.	
Clinical Phase:	IIb	
Trial Clinical Monitor:	 A large black rectangular redaction box covering the clinical monitor information.	
Co-ordinating Investigator:	 A large black rectangular redaction box covering the co-ordinating investigator information.	
Status:	Final Protocol (Revised Protocol (based on global amendment 5)	
Version and Date:	Version: 6.0	Date: 30-Jan-2018
Page 1 of 109		

Proprietary confidential information. © 2018 Boehringer Ingelheim International GmbH or one or more of its affiliated companies. All rights reserved. This document may not - in full or in part - be passed on, reproduced, published or otherwise used without prior written permission.
		

CLINICAL TRIAL PROTOCOL SYNOPSIS

Name of company: Boehringer Ingelheim	Tabulated Trial Protocol	
Name of finished product: NA		
Name of active ingredient: BI 655066		
Protocol date: 13 June 2014	Trial number: 1311.13	Revision date: 30-Jan-2018
Title of trial:	An open label extension trial assessing the safety and efficacy of BI 655066/ ABBV-066/risankizumab administered subcutaneously in patients with moderate to severe chronic plaque psoriasis.	
Co-ordinating Investigator:		
Trial site(s):	Multicenter, multinational	
Clinical phase:	IIb	
Objective(s):	Long term safety and efficacy of BI 655066/ ABBV-066/risankizumab during open-label treatment in patients with moderate to severe chronic plaque psoriasis.	
Methodology:	Open label extension.	
No. of patients:	100 (estimated)	
total entered:	100 (estimated)	
each treatment:	All patients will receive 90 mg BI 655066/ ABBV-066/risankizumab for 12 weeks, followed by 90 or 180 mg every 12 weeks depending on efficacy	
Diagnosis :	Moderate to severe chronic plaque psoriasis.	
Main criteria for inclusion:	Patients with moderate to severe chronic plaque psoriasis, who have successfully completed the preceding trial 1311.2. Successful completion of preceding trial is defined as either of the following: a. Completion of the entire follow up period, thus reaching EOS visit. b. Loss of response, defined as decrease in response to <PASI50 at any time from week 24.	

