2.2 TRIAL OBJECTIVES

The overall purpose of this open label extension (OLE) trial is to assess long-term safety and efficacy (durability of response) of BI 655066 in patients with moderate to severe chronic plaque psoriasis. In addition, this study will provide an opportunity for subjects to have extended access to a proven active therapy for approximately four years administration.

The primary objective of the study is to investigate safety of BI 655066, in patients with moderate to severe chronic plaque psoriasis, receiving long-term treatment.

Additional objectives of this study are to further investigate long-term efficacy, tolerability, pharmacokinetics, pharmacodynamics and immunogenicity of BI 655066.

Study endpoints are listed in [Section 5](#).

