3. DESCRIPTION OF DESIGN AND TRIAL POPULATION

3.1 OVERALL TRIAL DESIGN AND PLAN

This open label extension trial (OLE), investigates the additional safety and efficacy of the 90 mg dose of BI 655066. Approximately 100 patients who meet the entry criteria are planned for inclusion in this trial, rolling over from the preceding 1311.2 trial. The treatment will be open label.

The treatment period will be approximately four years of administration starting with first administration of BI 655066 in either trial 1311.2 or 1311.13, followed by a 12 week follow up period. After 01-May-2018 and approval of this protocol amendment in each respective country, the next study visit will be the Extended EOS visit and therewith the last visit in this study. Patients who have completed the study without early treatment discontinuation will be offered to roll over to M15-997 open label extension (OLE) trial if they fulfill the in- and exclusion criteria for the M15-997 trial. Refer to [section 6.2.3](#).

Patients rolling over from the preceding trial 1311.2 will have to complete the treatment period in that trial, or complete the entire trial including the follow up period, reaching end of study. If, during the follow up period of the preceding trial (at any visit from week 24 and onwards in trial 1311.2) loss of response is detected, the patient can roll over in this extension trial. For this, loss of response is defined as $< \text{PASI}_{50}$.

Extended visit 1 of this trial should preferably be performed as a combined visit the same day as End of Study visit of 1311.2, or within an interim period of maximum 6 weeks thereafter.

1311.2

[figure not shown]
[figure not shown]

Figure 3.1:1 Guideline for roll over of patients from 1311.2 to OLE study 1311.13

After the approval of this protocol amendment in each respective country, all patients will follow [Flow Chart](#) (Extended Dosing Period) and receive 90mg BI 655066 subcutaneously at their Extended visit 1 (EV1). From EV1 onwards, BI655066 will be administered subcutaneously every 12 weeks during the trial. At EV2, if there is a lack of response, defined as <PASI90, the dose should be increased to 180mg for the remainder of the trial (see Fig 3.1.2).

For ongoing patients under the previous protocol amendment (Pre-Extended Dosing Period, [see Fig 3.1.3](#)), EV1 should be conducted at the following time points:

1. For ongoing patients with ≥ 12 weeks since the EOT visit: Conduct EV1 as soon as possible

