3.3.2 Inclusion criteria

1. Patients with moderate to severe chronic plaque psoriasis, who have successfully completed the preceding trial, 1311.2. Successful completion of preceding trial is defined as either of the following:
 - a. Completion of the entire follow up period, thus reaching End-of-study (EOS) visit.
 - b. Loss of response, defined as decrease in response to <PASI₅₀ at any time from week 24.
2. Patient must give informed consent and sign an approved consent form prior to any study procedures in accordance with Good Clinical Practice (GCP) and local legislation
3. Applicable only for female patients:

Negative urine pregnancy dip stick test at the roll-over visit, and if available at roll-over visit, negative

Serum β-Human Chorionic Gonadotropin (β-HCG) test ([cf. Section 3.3.4.1](#)).

In addition:

Women of childbearing potential (not surgically sterilized and between menarche and 1 year postmenopausal), that, if sexually active agree to use one of the appropriate medically accepted methods of birth control in addition to the consistent and correct use of a condom from date of the roll-over visit until 12 weeks after last treatment in this trial. Medically accepted methods of contraception's are: ethinyl estradiol containing contraceptives, diaphragm with spermicide substance, and intra-uterine-device.

OR

Proprietary confidential information.

© 2018 Boehringer Ingelheim International GmbH or one or more of its affiliated companies. All rights reserved.

This document may not - in full or in part - be passed on, reproduced, published or otherwise used without prior written permission.

Female patients which have vasectomized sexual partner(s) (vasectomy at least 1 year prior to enrolment).

OR

Surgically sterilized female patients with documentation of prior hysterectomy, tubal ligation or complete bilateral oophorectomy.

OR

Postmenopausal women with postmenopausal is defined as permanent cessation ≥ 1 year of previously occurring menses.

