7.2 NULL AND ALTERNATIVE HYPOTHESES

The primary hypothesis is that BI 655066 will sustain effectiveness without emergent safety issues during the extended visit period. This will be characterized descriptively. There is no formal statistical hypothesis testing in this study.

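### The SAP's efficacy outputs blend maintained response with recaptured response and omit the protocol's time-to-loss analyses, so as planned they do not answer the durability question

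*SAP*

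**What the plan says.** **Purpose.** Protocol 2.2 sets out to "assess long-term safety and efficacy (durability of response) of BI 655066". Protocol 7.2 hypothesises that "BI 655066 will sustain effectiveness without emergent safety issues during the extended visit period". The primary efficacy endpoint (Protocol 5.1.1.1) is PASI90 at week 48 of the Extended dosing period, scored against the 1311.2 baseline.

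**Who reaches EV1.** Protocol 3.3.2 admits patients by either of two routes. One is "Completion of the entire follow up period, thus reaching End-of-study (EOS) visit", with no response requirement. The other is a fall below PASI50 from week 24 of 1311.2. Patients already in this trial before the Extended period also move to EV1, some still on treatment and some not: "For ongoing patients with ≥ 12 weeks since the EOT visit: Conduct EV1 as soon as possible" (Protocol 3.1).

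**Planned efficacy outputs.** SAP 10.2 says "The following key efficacy variables will be summarized at Week 48" and lists PASI 50/75/90/100 and sPGA proportions. SAP 10.3 gives PASI and sPGA proportions at all Extended visits. SAP 10.1 groups efficacy by 1311.2 treatment group and uses observed cases. The only response-related split in the SAP, 90 mg throughout versus 180 mg at EV2 (SAP 11.2.1), is for selected safety tables.

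**Durability analyses in the protocol.** Protocol 5.1.1.3 and 7.3.2 plan Kaplan-Meier estimates of time to loss of PASI50, 75, 90 and 100 and of sPGA clear or almost clear. SAP section 10 contains none of these.

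**The concern.** Because PASI is always scored against the 1311.2 baseline, PASI90 at Week 48 has two meanings. For a patient at or above PASI90 at EV1 it is maintenance. For a patient below PASI90 at EV1 it is recapture on re-treatment. Only the first bears on durability.

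A proportion that mixes the two can stay level, or rise, while patients who entered in response are losing it. By-visit proportions show only the net of losses and recaptures. Grouping by 1311.2 arm does not help, since either state can occur within any arm. Protocol 4.1.2 shows how easily the two are merged: it treats PASI90 at EV2 as maintained response, although a patient who was below PASI90 at EV1 and reached it after one dose also meets that description.

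The risk is that a good Week 48 figure is reported as sustained effect when part of it is recapture.

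**Working it through.** **Inputs.** The plan gives no expected response rate, no share of patients in response at EV1 and no power or precision calculation, so there is no figure to reproduce. The planned size is about 100 patients (Protocol 3.3). The rates below are assumptions, shown over a range.

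**Identity.** Among patients evaluated at Week 48, let *p* be the overall PASI90 rate, *f* the share at or above PASI90 at EV1, *m* the Week 48 rate in those patients (maintenance) and *r* the rate in the others (recapture):

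p = f·m + (1 − f)·r

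Since *r* lies between 0 and 1:

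max(0, (p − (1 − f))/f) ≤ m ≤ min(1, p/f)

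**One overall rate, two readings.** Take p = 75% and f = 50%.
- m = 60%, r = 90%: 0.5 × 60 + 0.5 × 90 = 75%.
- m = 90%, r = 60%: 0.5 × 90 + 0.5 × 60 = 75%.

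**Range of maintenance rates compatible with the overall figure.**

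| Overall p | f = 20% | f = 40% | f = 60% | f = 80% |
|---|---|---|---|---|
| 70% | 0–100% | 25–100% | 50–100% | 62.5–87.5% |
| 80% | 0–100% | 50–100% | 67–100% | 75–100% |

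For example, at p = 70% and f = 40% the lower bound is (0.70 − 0.60)/0.40 = 0.25, and p/f = 1.75, so the upper bound is 1. At p = 80% and f = 80% the lower bound is (0.80 − 0.20)/0.80 = 0.75. At p = 90% and f = 60% it is (0.90 − 0.40)/0.60 = 0.83. The ambiguity narrows as *p* or *f* rises. Knowing *f* does not remove it, because the bounds already take *f* as known.

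**Precision after a split.** Exact (Clopper-Pearson) 95% intervals at about 75% observed, with assumed subgroup sizes:
- 75/100: 65% to 83%
- 52/70: 62% to 84%
- 38/50: 62% to 87%
- 22/30: 54% to 88%

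Crossing with 1311.2 arm would be too thin. Three dose regimens plus the comparator (Protocol 2.1) make 4 × 2 = 8 cells, or about 100/8 = 12.5 patients each if even. An observed 9/12 has an interval of about 43% to 95%.

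**Time origin.** SAP section 6.0 counts Rx days from the first risankizumab dose in this study. For a patient dosed in the Pre-Extended period that dose precedes EV1, so SAP Week 48 is not week 48 of the Extended period. Pairing EV1 status with SAP weeks would mix two clocks.

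**Prior exposure.** Protocol 2.3 says 75% of 1311.2 patients received BI 655066, which leaves about 25% who did not. If such a patient rolls directly into EV1, a PASI90 found there is not a response to BI 655066.

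**The case against.** The strongest objection is that the protocol already contains a direct durability analysis, the Kaplan-Meier time to loss of response, and that PASI is scheduled pre-dose at EV1. This stands against a reading that a reader might infer, namely that the trial cannot answer the durability question. The data are planned and the protocol names a suitable method. It does not rescue the SAP, which leaves that method out. Nor would copying the protocol text across be enough: a patient below PASI90 at EV1 has no PASI90 response to lose, and the protocol states neither who is at risk nor when time starts.

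A reader might also infer that everyone who entered through loss of response is below PASI50 at EV1. The documents do not support that. The criterion applies in 1311.2, and a patient dosed in the Pre-Extended period may have regained response before EV1. Classification should therefore rest on observed EV1 status, not on entry route.

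Three further objections have some weight.
- The lowest bounds are extreme. At 70% overall and f = 40%, a maintenance rate of 25% requires every entry non-responder to regain PASI90 while three quarters of responders lose it. The bounds show what the figure cannot exclude, not what is likely.
- For patients arriving off drug, EV1 status reflects persistence after dosing stopped. This is a reason to state the origin and describe it when reporting.
- Of the primary objective, Protocol 2.2 says "The primary objective of the study is to investigate safety of BI 655066", and the trial is descriptive. This limits the weight of the point. However, SAP 4.1 places long-term efficacy beside safety in its primary objective.

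**Conclusion.** The concern holds for the SAP as written. Its efficacy outputs are marginal proportions that mix maintenance with recapture, and the one protocol analysis aimed at durability is missing. The pooled Week 48 rate alone does not identify maintenance: under the assumed inputs the compatible range runs from uninformative (f = 20% at 70% or 80% overall) to moderately tight (75–100% at 80% overall and f = 80%). The actual range depends on two quantities that the documents do not give.

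The documents do not show that response is being lost, and they do not support the view that durability is beyond the trial's reach. The primary efficacy endpoint itself, PASI90 at Week 48, can still be summarised. What would lack support is a statement about sustained effect based on that figure. The point does not touch the safety objective and is worth acting on because the remedy is cheap.

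**What to change.** In SAP 10.2 and 10.3:

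1. Add a supplementary summary, overall and not crossed with 1311.2 arm, by observed pre-dose status at EV1. (a) At or above PASI90 at EV1: proportion at PASI90 at Week 48 and later Extended visits (maintenance). (b) Below PASI90 at EV1: proportion reaching PASI90 (recapture), with a sub-row for below PASI50. Do the same for sPGA using a score of 0 or 1 at EV1.
2. Restore the protocol's Kaplan-Meier time-to-loss analyses, restricted to patients in response at a stated origin.
3. Count weeks for these outputs from EV1, to match Protocol 5.1.1.1.
4. Report patients with no BI 655066 before EV1 separately.
5. Base durability statements on (a) and the time-to-loss analysis.

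The Flow Chart already schedules PASI and sPGA pre-dose at EV1, and its footnote 2 allows the 1311.2 end-of-study assessment to serve when the visits are combined. Dosed patients who never reached EV1 cannot be classified and should be counted as such. No new visits or data are needed. The cost is some programming and wider intervals in the split groups, for example 62% to 87% for 38/50 against 65% to 83% for 75/100.
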